5.1.3 BIOMARKER ENDPOINTS

- Change from baseline in tau PET signal at 24 months
- Change from baseline in CSF biomarkers t-tau and p-tau at 24 months
- Change from baseline in CSF amyloid biomarkers A β (1-x), A β (1-42), and A β (1-40) at 24 months
- Change from baseline in plasma amyloid biomarker (eg, A β (1-x)) at all assessments

- Change from baseline in plasma NFL and CSF NFL and Ng
- Change from baseline in vMRI parameters (eg, total hippocampal volume etc.) at 24 months using vMRI
- Change from baseline in the preservation of connectivity on fMRI at 24 months

If the available data for the analysis is not sufficient, the analyses for the following endpoints may not be performed or may be performed at only other visits than 24 months.

- Change from baseline in tau PET signal at 24 months
- Change from baseline in CSF biomarkers t-tau and p-tau at 24 months
- Change from baseline in CSF amyloid biomarkers A β (1-x), A β (1-42), and A β (1-40) at 24 months
- Change from baseline in CSF biomarkers (eg, NFL, and Ng)

The analyses for the following endpoint will be reported separately from the CSR because of the timing of data availability.

- Change from baseline in the preservation of connectivity on fMRI at 24 months

5.1.4 EXPLORATORY ENDPOINTS

- Time to change of concomitant AD treatment (ie, dose increase and/or initiation of treatment with Acetylcholinesterase inhibitors [AChEI] or memantine after randomization) by 24 months in the combined studies
- The proportion of subjects at 24 months who received dose increases and/or initiation of treatment with AChEI or memantine after randomization in the combined studies
- The rate of change over time (mean slope) based on NPI-10 item score over 24 months in the combined studies
- Change from baseline in NPI-10 item at 24 months in the combined studies
- Change from baseline in EQ-5D (subject self-reported, study partner self-reported, and subject measured by proxy) and QOL-AD (subject and study partner) at 24 months in the combined studies
- Change from baseline in Zarit's Burden Interview at 24 months in the combined studies

5.2 STUDY SUBJECTS

5.2.1 Definitions of Analysis Sets

The definitions of the analysis data sets are:

- The Randomized Set is the group of subjects who are randomized to study drug.
- The Safety Analysis Set is the group of subjects who receive at least 1 dose of study drug and have at least 1 postdose safety assessment. Safety Analysis Set will be used in the statistical analyses for safety. In the event that a subject received study drug different from the one to which this subject was randomized, the subject's safety data will be analyzed "as treated."
- The Full Analysis Set (FAS) is the group of randomized subjects who receive at least 1 dose of study drug and have baseline and at least 1 postdose primary efficacy measurement.
- The Per Protocol Analysis Set (PPS) is the subset of subjects in the FAS who sufficiently comply with the protocol. PPS will be used to conduct a sensitivity analysis of the primary efficacy endpoint. The criteria for exclusion from PPS are listed below:
 - MMSE <24 or CDR global score \neq 0.5 or CDR Memory Box score < 0.5 at screening
 - Condition that may contribute to cognitive impairment at screening
 - vascular dementia, lewy body dementia, PD, multiple sclerosis, epilepsy in medical history
 - Hachinski Score >4
 - Brain MRI exclusions
 - BMW [Section 4](#) Other MRI Abnormalities exclusions including:
 - Superficial siderosis
 - Lacunar infarct (2 or more)
 - Stroke involving a major vascular territory
(Defined by safety MRI data)
 - ISLT total recall and delayed recall impairment < 1 SD from age-adjusted norms at screening
 - Negative for amyloid pathology for all assessments performed at screening, ie PET and/or CSF.
 - Subject <50 or >85 years of age at consent
 - Subject was receiving AChEIs or memantine or both for AD but had not been on a stable dose for at least 12 weeks prior to baseline
 - At screening
 - Thyroid stimulating hormone (TSH) > upper limit of normal (ULN)

- Vitamin B12 < lower limit of normal (LLN) and methylmalonic acid MMA >0.41µm/L (if MMA available)
 - Illiteracy in medical history
 - Study drug compliance
 - < 67% up to planned last dose
- The PK Analysis Set is the group of subjects with at least 1 quantifiable elenbecestat plasma concentration with a documented dosing history.
- The PD Analysis Set is the group of subjects who have sufficient PD data to derive at least 1 PD parameter. The separate analysis set will be prepared for amyloid PET, tau PET, plasma, CSF, and vMRI assessments.

The number (percent) of subjects included in each analysis set will be presented by treatment group and combined total for each analysis set.

The subjects who enroll into the OLE phase and receive at least 1 dose of OLE study drug will be considered as “All Safety Subjects” for OLE, which will be used for OLE tables mainly.

5.2.2 Subject Disposition

The number of subjects screened, the number (percent) of subjects who failed screening, and the reasons for screen failure will be summarized, based on data reported on the Screening Disposition electronic case report form (eCRF). The primary reasons for screen failures (did not meet inclusion or met exclusion criteria, adverse event (AE), lost to follow-up, withdrawal of consent, and other) will be presented. The distribution of the number of randomized subjects enrolled by each site, country, and region will be summarized for each randomized treatment group and combined total.

Study Completion: the number (percent) of randomized and treated subjects who completed the study and who withdrew from the study will be summarized according to the primary reason for withdrawal and secondary reason(s) for withdrawal, based on data reported on the Subject Disposition (Study Phase) case report form (CRF). The number (percent) will be presented by treatment group and total subjects; randomized, not treated, treated, who completed the study, and withdrew from the study. The primary reasons for early withdrawal from the study are: AE, lost to follow-up, subject choice, inadequate therapeutic effect, withdrawal of consent, pregnancy, study terminated by sponsor, and other. The secondary reasons for early withdrawal from the study are: AE, subject choice, inadequate therapeutic effect, and other. This table will be summarized on the All Randomized Subjects, the Safety Analysis Set, and the FAS.

Completion of Study Treatment: the number (percent) of randomized and treated subjects who completed study drug and who discontinued early from study drug will be summarized according to the primary reason for early discontinuation (ED) and also according to secondary reason(s) for discontinuation, based on data reported on both the Subject Disposition (Study Phase) eCRF and ED from Study Drug eCRF. The number (percent) will be presented by treatment group and total subjects; randomized, not treated, treated, who completed study drug, and discontinued from study drug. The primary reasons for early discontinuation from the study drug are: AE,

subject choice, inadequate therapeutic effect, pregnancy, and other. The secondary reasons for early discontinuation from the study drug are: AE, subject choice, inadequate therapeutic effect, and other. This table will be summarized on the All Randomized Subjects, the Safety Analysis Set, and the FAS.

The subject disposition for the OLE phase will be summarized in the same way.

5.2.3 Protocol Deviations

A listing of subjects with major protocol deviations will be provided by subject along with the description of the protocol deviation. Protocol deviations will be identified prior to database lock. Major protocol deviations will be summarized by treatment group and combined total.

5.2.4 Demographic and Baseline Characteristics

Demographic and baseline characteristics for the Safety Analysis set and FAS will be summarized by treatment group using descriptive statistics.

Continuous demographic and baseline variables include: age (years), baseline height (cm) and weight (kg), body mass index (BMI) (kg/m^2), CDR-SB score, ADAS-cog₁₁, ADAS-cog₁₄, ADAS-cog₁₄ Word List, ADCOMS, MMSE, ISLT z-score (total recall, delayed recall), Cogstate Brief Battery (CBB) z-score (accuracy of one-card learning, speed of one-back memory, speed of detection, speed of identification), FAQ, years since onset of cognitive impairment symptoms, and years since disease diagnosis, education in years.

Categorical variables include: age group (<65, ≥ 65 to <80, and ≥ 80), sex, race, ethnicity, region, concurrent AD medication use (yes, no), clinical disease staging (MCI due to AD, early stages of mild AD), apolipoprotein E (*ApoE*) 4 status, CDR Memory Box score and CDR-SB score (0 to 1.5, 2 to 3.5, 4 to 5.5, 6 or more).

Date of disease diagnosis will be defined as the date of current diagnosis on the Cognitive Impairment History and Current Diagnosis eCRF or the date of diagnosis of mild cognitive impairment on the Medical History and Current Medication Condition eCRF, whichever is earlier.

Region, concurrent AD medication use, and clinical disease staging will be summarized using the actual classification, not the interactive voice and web response system (IxRS) classification.

Baseline in PD/biomarkers for All Randomized Subjects will be summarized by treatment group and combined total using descriptive statistics.

For OLE, demographic and baseline characteristics for All Safety Subjects will be summarized using descriptive statistics.

MEDICAL HISTORY

The medical history verbatim descriptions (investigator terms from the CRF) will be classified into standardized medical terminology using the Medical Dictionary for Regulatory Activities (MedDRA). Medical history will be coded to the MedDRA lower level term (LLT) closest to the verbatim term. The linked MedDRA preferred term (PT) and primary system organ class (SOC) will also be captured in the database. The number (percent) of subjects will be presented by preferred term and treatment group.

5.2.5 Prior and Concomitant Therapy

All investigator terms for medications recorded in the eCRF will be coded to an 11-digit code using the World Health Organization Drug Dictionary (WHO DD). The number (percentage) of subjects who took prior, concomitant, current and treatment-emergent concomitant medications will be summarized on the Safety Analysis Set by treatment group, Anatomical Therapeutic Chemical class, and WHO DD preferred term (PT). Prior medications will be defined as medications that stopped before the first dose of study drug. Concomitant medications will be defined as medications that (1) started before the first dose of study drug and were continuing at the time of the first dose of study drug, or (2) started on or after the date of the first dose of study drug up to the date of the last dose. Current medication will be defined as medications that started before the first dose of study drug and were continuing at the time of the first dose of study drug. Treatment-emergent concomitant medication will be defined as medications that started on or after the date of the first dose of study drug up to the date of the last dose. All medications will be presented in subject data listings. Medications taken during the 12-week Follow-Up Period will also be recorded.

Prior and concomitant therapies for AD will be summarized separately.

Subjects' status on AD medications will be summarized by overall and each clinical disease staging.

5.2.6 Treatment Compliance

Treatment compliance (%) will be calculated for Safety Analysis set as follows:

$$\frac{\text{Total number of tablets dispensed} - \text{Total number of tablets returned}}{\text{Planned Total number of tablets to be taken}} * 100\%$$

Compliance will be calculated in two ways: compliance up to the planned date of last dose of study drug (compliance rate during treatment), and overall compliance rate. For compliance rate during treatment, the planned total number of tablets to be taken up to the planned date of last dose of study drug will be used as denominator. Overall compliance rate will be calculated as the 24-month compliance by assuming each subject has been followed through 24 months (729 days) in the study; a subject will be considered to take no study drug after study drug discontinuation until the end of 24 months. For overall compliance rate, 729 will be used as denominator. '999' in total number of tablets dispensed at visit is considered as 0 in the above

calculation. '999' in total number of tablets returned at visit is considered that all tablets dispensed would be returned at visit. If planned total number of tablets to be taken at visit is missing, it will be imputed by total number of tablets dispensed at visit unless total number of tablets dispensed and total number of tablets returned at visit is same.

Treatment compliance will be summarized using descriptive statistics by treatment group. Subjects will also be categorized by compliance criteria <67%, 67% to 100%, >100% to 120%, and >120%.

5.2.7 Stratification factor status

IxRS versus CRF Stratification Factors (concurrent AD medication use, clinical disease staging, region) will be summarized by treatment.

5.3 DATA ANALYSIS GENERAL CONSIDERATIONS

5.3.1 Pooling of Centers

This study has used region as a stratification factor for randomization, therefore, there is no plan to pool any other type of centers or sites.

The regions and corresponding countries that might be included and are grouped together in a particular region are:

1. North America: US, and Canada
2. Western Europe (including Oceania region and South Africa): Australia, Austria, Denmark, Finland, France, Germany, Italy, Portugal, South Africa, Spain, and United Kingdom
3. Eastern Europe: Bulgaria, Croatia, Czech Republic, Greece, Hungary, Poland, Russian Federation, and Slovakia
4. Japan
5. China
6. Other Asian countries/regions: Singapore, South Korea, and Taiwan
7. South America: Argentina, Chile, and Mexico

Czech Republic is incorrectly listed in IxRS as part of Western Europe and Australia is incorrectly listed in IxRS as part of Other Asian countries (both for E2609-G000-301). The correct list shown above will be used for the any analyses except the adjustments for covariates of interest to follow intent to treat (ITT) principle.

5.3.2 Adjustments for Covariates of Interest

The primary, secondary, and exploratory efficacy endpoints will include the stratification variables (region, concurrent AD medication use, clinical disease staging), *ApoE4* status, and baseline value of the endpoint (if applicable) as covariates. For mixed-effects models for repeated measures (MMRM), the baseline-by-visit interaction will also be included. To follow ITT principle, the classification used at randomization will be used for the adjustments for covariates of interest.

5.3.3 Multiple Comparisons/Multiplicity

The primary and key secondary endpoints will be tested using a sequential testing procedure at a significance level of 2-sided $\alpha = 0.05$, ie, any test will start only if the test with higher hierarchical order is significant. The hierarchical order for these endpoints is:

1. Change from baseline in the CDR-SB at 24 months in the combined studies (primary endpoint)
2. Change from baseline in ADCOMS at 24 months in the combined studies
3. Change from baseline in amyloid PET SUVR at 24 months for brain amyloid levels in the combined studies
4. Change from baseline in amyloid PET SUVR at 24 months for brain amyloid levels in the individual studies

The 4th endpoint will be excluded because of smaller sample size than original plan.

Analyses on other secondary, biomarker and exploratory endpoints will be conducted without adjustment for multiplicity.

5.3.4 Examination of Subgroups

Subgroup analysis will be performed for the primary, secondary efficacy endpoints, and biomarker endpoints. The subgroups include:

- age (<65, 65 to <80, and ≥ 80 years)
- sex
- race
- ethnicity
- region ([section 5.3.1](#))
- concurrent AD medication use (yes, no) at baseline

- clinical disease staging (MCI due to AD, early stages of mild AD) at baseline
- *ApoE4* status
- baseline CDR Memory Box score
- very mild subjects (baseline CDR-SB \leq 1.5 and baseline MMSE \geq 27)
- baseline amyloid PET SUVR 1.2 to 1.6
- amyloid PET tracer (Florbetapir, Florbetaben, and Flutemetamol; only for amyloid PET SUVR)

For concurrent AD medication use, clinical disease staging, and region, the actual classification (not the IxRS classification) will be used.

As described in [Section 5](#) Statistical methods, the efficacy will also be evaluated within each study (E2609-G000-301 and E2609-G000-302).

Forest plot for primary and key secondary endpoint (only ADCOMS) will be generated to visually display the treatment difference with 95% confidence interval, no significance tests will be performed in the subgroups.

5.3.5 Handling of Missing Data

Efficacy endpoints

The primary endpoint will be analyzed using MMRM assuming missing at random (MAR). The same method will be used for key secondary endpoints, other secondary endpoints, exploratory endpoints and biomarker endpoints if appropriate.

In addition, all missing values will be imputed using multiple imputation assuming MAR with analysis of covariance (ANCOVA) as sensitivity analysis for primary analysis. The detailed programs are shown in [Section 9](#).

Clinical Assessment

If any item is missing within the CDR, ADCOMS, ADAS-cog₁₁, ADAS-cog₁₄, MMSE, FAQ, and ADAS-cog₁₄ Word List (immediate recall and delayed recall) then their respective total scores will be missing.

Laboratory values

If the values include non-numerical symbols “>”, “<”, “<=” and “>=”, they will be imputed using the following rule.

- For < values impute with value - 1
- For > values impute with value + 1
- For >= values or <= values impute with value

If the least significant digit of the value is after the decimal point, increase/decrease by the smallest unit of that digit (ex. for, “>7.3”, use 7.4 which is calculated by $7.3 + 0.1$).

Plasma/CSF PD/Biomarkers

Values >upper limit of quantification (ULOQ) or < lower limit of quantification (LLOQ) will be imputed using ULOQ or LLOQ respectively.

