5.1.2 SECONDARY ENDPOINTS

The key secondary endpoints of the study are as follows

- Change from baseline in ADCOMS at 24 months in the combined studies
- Change from baseline in amyloid PET SUVR at 24 months for brain amyloid levels in the combined studies
- Change from baseline in amyloid PET SUVR at 24 months for brain amyloid levels in the individual studies

The other secondary endpoints of the study are as follows

- Change from baseline in the CDR-SB at 24 months for subjects enriched by baseline PET SUVR, eg, between 1.2 and 1.6, in the combined studies
- Change from baseline in the ADCOMS at 24 months for subjects enriched by baseline PET SUVR, eg, between 1.2 and 1.6, in the combined studies
- The rate of change over time (mean slope) based on CDR-SB score over 24 months in the combined studies

- Time to worsening of CDR scores by 24 months (eg, the worsening of global CDR score is defined as an increase from baseline by at least 0.5 points on the global CDR scale on 2 consecutive scheduled visits at which global CDR is undertaken) in the combined studies
- Time to conversion to dementia by 24 months for subjects who were not clinically staged as dementia at Baseline based on clinical diagnosis in the combined studies
- Change from baseline in CDR-SB at 27 months (ie, 24 months of treatment plus 3 months posttreatment follow-up) in the combined studies
- Change from baseline in ADAS-cog₁₄, MMSE, and FAQ at 24 months in the combined studies
- Change from baseline in ADAS-cog₁₄ Word List (immediate recall and delayed recall) at 24 months in the combined studies

Based on the DSMB analyses, the change from baseline in ADAS-cog₁₁ will be added as one of other secondary endpoints.

The following secondary endpoint will be added to evaluate the change after last dose instead of the change from baseline in CDR-SB at 27 months described above.

- Change from last dose to follow-up in CDR-SB, ADCOMS, ADAS-cog₁₁, ADAS-cog₁₄, MMSE, ADAS-cog₁₄ Word List (immediate recall and delayed recall) in the combined studies

As the study E2609-G000-301 and study E2609-G000-302 were terminated early, the sample size for amyloid PET SUVR is smaller than originally planned. Therefore the following key secondary endpoint will be removed.

- Change from baseline in amyloid PET SUVR at 24 months for brain amyloid levels in the individual studies

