The other continuous secondary efficacy endpoints will be analyzed using the same MMRM model as the primary efficacy analysis to compare elenbecestat 50 mg versus placebo on the FAS, using baseline value corresponding to the response variable in the model. These endpoints include:

- Change from baseline in the CDR-SB at 24 months for subjects enriched by baseline PET SUVR, eg, between 1.2 and 1.6, in the combined studies
- Change from baseline in the ADCOMS at 24 months for subjects enriched by baseline PET SUVR, eg, between 1.2 and 1.6, in the combined studies
- Change from baseline in ADAS-cog₁₁, ADAS-cog₁₄, MMSE, and FAQ at 24 months in the combined studies
- Change from baseline in ADAS-cog₁₄ Word List (immediate recall and delayed recall) at 24 months in the combined studies

The following amyloid PET mean composite SUVR in centiloid scale ([Adamczuk, 2019](#)) will be used to enrich the population, extrapolated from the 1.2 to 1.6 SUVR calculated for Florbetapir ([Dhadda, 2018](#)) : 37.234 to 119.522 (equivalent to 1.198633 to 1.667324 in Florbetaben and 1.212557 to 1.777799 in Flutemetamol) (Adamczuk [2019])

With regard to the change from baseline in ADAS-cog₁₄ Word List, it includes the immediate and delayed recall tasks, their scores will be part of the ADAS-cog₁₄ assessment (Item 1 and 4).

For ADAS-cog₁₁, ADAS-cog₁₄, MMSE, FAQ, and ADAS-cog₁₄ Word List (immediate recall and delayed recall), the MMRM analysis will be conducted on FAS, by censoring the data after intercurrent events (treatment discontinuation, and initiation/change of AD medications) as sensitivity analyses.

The MMRM using the change from baseline at last on treatment visit and 12 week Follow-up visit will be conducted based on the subjects in FAS who have the assessments at both visits to evaluate the change after last dose in CDR-SB, ADCOMS, ADAS-cog₁₁, ADAS-cog₁₄, MMSE, and ADAS-cog₁₄ Word List (immediate recall and delayed recall) instead of the analysis for the change from baseline in CDR-SB at 27 months. The same MMRM as the primary efficacy analysis (except excluding baseline by visit interaction) will be used with appropriate contrast to evaluate the difference between last on treatment visit and 12 week Follow-up visit by each treatment group.

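### The change-after-last-dose MMRM in SAP v2.0 is fitted to complete pairs only, so it reduces to a paired mean and makes no use of the missing-at-random assumption

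*SAP*

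**What the plan says.** All references are to SAP v2.0.

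- Section 5.3.5 names the MMRM under MAR for the primary endpoint, then adds: "The same method will be used for key secondary endpoints, other secondary endpoints, exploratory endpoints and biomarker endpoints if appropriate".
- Section 5.1.2 introduces the endpoint: "The following secondary endpoint will be added to evaluate the change after last dose instead of the change from baseline in CDR-SB at 27 months". It covers CDR-SB, ADCOMS, ADAS-cog11, ADAS-cog14, MMSE and the ADAS-cog14 Word List.
- Section 5.4.2, under other continuous endpoints, says the analysis "will be conducted based on the subjects in FAS who have the assessments at both visits to evaluate the change after last dose".
- On the model, 5.4.2 says: "The same MMRM as the primary efficacy analysis (except excluding baseline by visit interaction) will be used with appropriate contrast". The contrast is taken "to evaluate the difference between last on treatment visit and 12 week Follow-up visit by each treatment group".
- Section 5.4.1 specifies an unstructured covariance for that model. For the primary endpoint it uses all observed post-baseline data.
- Section 3.2 requires the 12-week follow-up of every subject, including those who stop study drug early.
- Section 8.2 defines the last on-treatment value as the last post-baseline assessment on or before the last dose.

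**The concern.** Because follow-up is required of everyone, a subject with a last on-treatment score and no 12-week score has missing data. An MMRM earns its MAR justification by keeping such subjects, so that the observed score informs the mean at the unobserved visit. Section 5.4.2 removes them before the model is fitted. What remains carries the name of the primary model but is a complete-case analysis. The multiple-imputation analysis in 5.4.1 covers only the primary endpoint, and 5.4.2 gives this endpoint no missing-data sensitivity analysis.

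The endpoint is the one that describes what happens to cognition once drug stops. The DSMB form of 11 September 2019 recommended termination and cited detrimental trends on some cognitive measures by 18 months. Readers will therefore look at the off-drug change in each arm, and will compare the arms informally even though the contrast is within arm.

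**Working it through.** **Plan's own figure.** The SAP states no figure for this analysis. The section 4 inputs used below do reproduce its sample size. The effect is 0.25 x 1.46 = 0.365 with SD 2.05, so n = 2 x (1.960 + 1.282)^2 x 2.05^2 / 0.365^2 = 663 per arm. Then 663 / 0.70 = 948 per arm, or 1896 in total against 1900 stated.

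**Step 1: what the model reduces to.** For each complete pair, let L be the change from baseline at the last on-treatment visit, F the change at follow-up, and D = F - L.

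- Mean of L = arm mean + covariate terms (baseline score, region, staging, AD medication, ApoE4).
- Mean of D = arm effect only, because covariates with the same coefficient at both visits cancel.

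The regressors for D are a subset of those for L. With unstructured covariance and no missing values, generalised least squares for D then equals ordinary least squares, which is the arm mean of D. A simulated data set confirmed it: the MMRM contrasts were 0.39094 and 0.27274, and the raw paired means were 0.39094 and 0.27274.

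**Step 2: when this is biased.** To first order,

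bias = slope of D on L x (mean of L among returners - mean of L among all).

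Both factors must be non-zero. When return was simulated to depend on L but D was independent of L, the bias was -0.0005. When return was unrelated to L, it was about 0.

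**Step 3: size, first set of assumptions.** None of these values is in the SAP.

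- 15% to 45% without follow-up.
- Odds of non-return 1.3 to 2.0 per SD of L, with SD 1.6 points.
- Slope of D on L from -0.3 (regression to the mean) to +0.1 (faster decliners keep declining).

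The shift in mean L among returners is -0.06 to -0.45 points, which gives:

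| Shift in L | Slope | Bias (CDR-SB points) |
|---|---|---|
| -0.45 | -0.3 | +0.135 |
| -0.45 | -0.1 | +0.045 |
| any | 0 | 0 |
| -0.45 | +0.1 | -0.045 |

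At the SAP's 30% dropout rate, odds ratio 2.0 and slope -0.3, the bias is +0.09.

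**Step 4: size, second set.** SD is 2.05 from section 4. Assumed: true change 0.2, about 70% return, and log-odds of return falling 0.5 per CDR-SB point. That is an odds ratio of exp(0.5 x 2.05) = 2.8 per SD, a stronger dependence than in step 3. Return depends on the score in both arms.

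| Correlation between visits | Complete-pair bias, two arms | Same MMRM, incomplete pairs kept |
|---|---|---|
| 0.70 | +0.149, +0.129 | +0.004, -0.017 |
| 0.80 | +0.105, +0.091 | +0.011, -0.008 |
| 0.90 | +0.042, +0.048 | -0.004, +0.001 |
| 0.95 | +0.027, +0.027 | +0.001, +0.001 |

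The last column is simulation noise around zero. If only the active arm's return depended on the score, only that arm was biased (+0.02 to +0.15).

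**Step 5: benchmark.** At the placebo rate in section 4, 1.46 / 24 x 3 = 0.18 points per 3 months. CDR visits are about 91 days apart (Table 4), so after an early stop the pair may span about 84 to 84 + 91 = 175 days. Over the 728 days from Day 1 to Day 729, that is 1.46 x 84 / 728 = 0.17 to 1.46 x 175 / 728 = 0.35 points.

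**The case against.** **No contradiction with 5.3.5.** A reader might infer that 5.4.2 breaks a rule set in 5.3.5. The documents do not support that. The general sentence in 5.3.5 is qualified as applying where appropriate, and 5.4.2 then gives a specific rule that is still an MMRM. This objection stands: the weakness lies in 5.4.2 alone.

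**Selective return is not enough.** A reader might also infer that the estimate is biased whenever return depends on the last score. Step 2 shows that the later change must correlate with that score too. Nor does the SAP say that subjects who decline most are least likely to return. Section 3.2 requires follow-up of everyone, and because both studies were terminated early, some subjects stopped for reasons unrelated to their scores.

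**Size and sign are open.** The extreme of +0.135, about 74% of 0.18, needs the highest missing rate, the strongest dependence and the steepest slope together. Against a pair spanning 175 days the same bias is 0.135 / 0.35 = 39%. This stands.

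**Low stakes, and a defensible definition.** The endpoint is outside the hierarchy in 5.3.3, has no decision rule, and the dropped on-treatment scores still enter the visit-wise analyses. Restricting change after last dose to subjects with both values is at least transparent, and the alternative relies on MAR for off-drug scores nobody saw. The first part limits the importance. The second does not rescue the rule: complete pairs also rest on an untestable assumption, and a stronger one, because the observed on-treatment score is not allowed to explain non-return.

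**Conclusion.** The point holds as a modest, inexpensive improvement to 5.4.2. The reduction to a paired mean is exact and needs no assumption beyond the model as written. Whether it causes bias depends on two conditions that the SAP does not inform; if either is absent, the complete-pair estimate is unbiased. Under the assumptions shown, the bias per arm lies between about -0.045 and +0.15 CDR-SB points, includes zero, and is small when the two visits correlate at about 0.95. The benchmark is 0.18 points over 3 months, rising to about 0.35 if the pair spans nearly 6 months. Keeping incomplete pairs in the same model removes the bias when return depends only on the last on-treatment score. Neither approach protects against non-return that depends on the unseen off-drug score. No conclusion on the primary or key secondary endpoints is affected.

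**What to change.** In 5.4.2, replace the restriction to subjects with both assessments. Fit the same two-visit unstructured MMRM to all FAS subjects with a last on-treatment assessment, whether or not the 12 week Follow-up assessment is present, and take the within-arm contrast from that fit. Keep the complete-pair result as a sensitivity analysis, and report the number in each arm with and without a follow-up assessment so that readers can judge how much the two could differ.

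The cost is one change of wording, one dataset flag and one extra model run per scale. No new data are needed. The price is reliance on MAR for unseen off-drug scores, which should be stated next to the result.
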